5 ENDPOINTS AND COVARIATES

The endpoints and covariates that will be defined by the data abstracted from the medical records are described in this section.

PFIZER CONFIDENTIAL

CT24-WI-GL03-RF03 2.0 Non-Interventional Statistical Analysis Plan For Secondary Data Collection Study
01-Jun-2020
Page 10 of 29

5.1 EFFICACY/EFFECTIVENESS ENDPOINT(S)

As the primary endpoint, OS will be defined as time in months from initiation of 1L therapy to death from any cause. For details on endpoint definition, please refer to [Table 5-1](#).

5.2 SAFETY ENDPOINTS

Not applicable.

5.3 EXPLORATORY ENDPOINTS

As exploratory endpoints, [CCI](#) [REDACTED], and time to chemotherapy will be assessed. For details on endpoint definitions, please refer to [Table 5-1](#).

5.4 STUDY ENDPOINTS

The endpoints or study outcomes to be analyzed for each study objective and the associated definitions are described in [Table 5-1](#).

Table 5-1. Definition of Endpoints

Variable	Role/objective	Definition
Overall survival in 1L	Primary	The time in months from initiation of 1L therapy (palbociclib + AI or AI alone) to all-cause death . Patients who did not die will be censored at the end of study follow-up as defined in Section 2.1 .
CCI		[REDACTED]

Variable	Role/objective	Definition
CCI		
Time to chemotherapy	Exploratory	Time in months from the study index date to first initiation of chemotherapy in any subsequent therapy lines. Patients who did not initiate chemotherapy treatment as of last follow-up will be censored at the end of the follow-up.

1L = first line; AI = aromatase inhibitor; CDK4/6 = cyclin-dependent kinase 4 and 6;

CCI

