Data from at least 2 observational studies have shown possible OS benefits in relatively older patient populations. Results from P-Reality-X, a real-world evidence study conducted using data from the Flatiron electronic health record (median age, 70 years for palbociclib treatment group), also reported improved OS, specifically for patients receiving palbociclib + AI compared with AI alone. After stabilized inverse probability of treatment weighting, median OS (95% CI) is significantly longer among palbociclib compared with AI recipients (49.1 [45.2-57.7] vs. 43.2 [37.6-48.0] months; hazard ratio, 0.76 [95% CI, 0.65-0.87]; $P < 0.0001$) (Rugo et al., 2022a). In another study of older

patients (median age, 74 years for both the treatment arms: palbociclib + letrozole and letrozole alone), the palbociclib group was shown to have significantly better OS than the letrozole alone group (hazard ratio, 0.55 [95% CI, 0.42-0.72]; $P < 0.001$) (Rugo et al., 2023). In a recent observational study of an Medicare population of patients with diagnosis of *de novo* HR+/HER2- mBC using data from the Surveillance, Epidemiology, and End Results (SEER)-Medicare during an early period of CDK4/6 inhibitors use (2015-2017), Goyal et al. (2023) analyzed the effect of the CDK4/6 inhibitors (as a class) on OS and reported that combination therapy with ET and a CDK4/6 inhibitor is independently associated with improved OS compared with ET alone (hazard ratio, 0.59; 95% CI, 0.42-0.82). The majority ($\geq 90\%$) of patients in the CDK4/6 inhibitor group (median age, 70 years) in this study were taking palbociclib (Trapani and Mayer, 2023).

Because the evidence from real-world populations are often underrepresented in clinical trials (Lewis et al., 2003; Loree et al., 2019; Murthy et al., 2004; Talarico et al., 2004), and because 2 additional years of SEER-Medicare data have now become available allowing for more sample size and additional follow-up we seek to understand current data on potential survival benefits among the primary cohort of patients treated with palbociclib + AI compared with AI alone after *de novo* mBC diagnosis. A description of the SEER-Medicare database is provided in Section 2.1.

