2.1 STUDY DESIGN

[figure not shown]
This study will encompass a retrospective cohort analysis using clinical and administrative claims data from the linked SEER-Medicare database (providing SEER data are available through 2019 and linked Medicare claims are available through 2020) for patients with diagnosis of HR+/HER2- mBC at initial presentation. The study will assess the rates of OS in patients 65 years or older with diagnosis of *de novo* mBC from 2015-2019 who initiated 1L systemic therapy with palbociclib + AI or AI alone following the first approval of palbociclib in February 2015. **Figure 2-1** presents a graphical schema of the study design (drawn for a hypothetical patient and not to scale).

Based on the study schema presented below, the following key study definitions will apply:

- **De novo mBC diagnosis date window:** From 1 February 2015 through 31 December 2019
- **Study index date:** The date of 1L treatment initiation with palbociclib + AI or AI alone after the *de novo* mBC diagnosis
- **Case selection window:** From 1 February 2015 through 30 June 2020 – for the date of 1L treatment initiation (study index date)

- **Baseline period:** The 6-month period before the study index date (to assess patient baseline demographic and clinical characteristics)
- **Study follow-up:** All patients will be followed from their study index date through the earliest of the following: death, disenrollment from Medicare Part A (hospital insurance), Part B (medical insurance), or Part D (prescription drug insurance), enrollment in a health maintenance organization (HMO) plan, or end of the study database (31 December 2020).
- **Overall study period:** From 1 August 2014 (to allow up to 6 months of look back period for any patient with index date in February 2015) through 31 December 2020 (accounting for a minimum 6 months of potential follow-up for any patient with index date in June 2020).

Figure 2-1. Study Design Schematic (Depiction for a Hypothetical Patient)

AI = aromatase inhibitor; HER2- = human epidermal growth factor receptor 2-negative; HR+ = hormone receptor-positive; mBC = metastatic breast cancer.

Note: Figure not drawn to scale.

Study Population

The study population will represent Medicare beneficiaries (men or women) with diagnosis of HR+/HER2- mBC at initial presentation (i.e., de novo), as identified in the SEER-Medicare database.

Data Source

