2.2 STUDY OBJECTIVES

[figure not shown]
Following the work of Goyal *et al.* (2023), this retrospective, noninterventional study aims to assess OS in Medicare patients with HR+/HER2- *de novo* mBC who initiated 1L treatment with palbociclib + AI combination therapy versus AI alone. Specifically, the key objectives of this study are as follows:

Primary objective:

- To compare OS of 1L palbociclib + AI versus AI alone for women or men with *de novo* HR+/HER2- mBC in the SEER-Medicare database who are ≥ 65 years old

Exploratory objectives:

CCI

- To measure time to chemotherapy, if enough follow-up time is available to assess this measure.

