7 STATISTICAL METHODOLOGY AND STATISTICAL ANALYSES

7.1 STATISTICAL METHODS

Means with standard deviations, medians with interquartile range, and min/max values will be provided for continuous variables when performing descriptive analysis of continuous data. Numbers and percentages will be provided for dichotomous and polychotomous variables when performing descriptive analysis of categorical data. Baseline patient demographics (e.g., age, race, marital status) and clinical characteristics (e.g., metastatic sites, NCICI) will be descriptively analyzed and reported. Unadjusted and/or weighted Kaplan-Meier curves will be drawn to illustrate time-to-event endpoints.

All analyses will be performed separately for the primary and exploratory objectives described in Section 2.2, and any computations and generation of tables, listings, and data for figures will be conducted using SAS statistical software, version 9.4 or later (SAS Institute; Cary, North Carolina).

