PSM: In the PSM technique, each patient in the palbociclib +AI cohort will be matched to a patient in the AI alone cohort using a 1-to-1 matching with no replacement, using the nearest neighbor method to match by closest propensity scores (with a caliper of 0.01). As described above, median OS, landmark probabilities of event at various timepoints, and 95% CI for the matched cohorts will be assessed, and the hazard ratio will be assessed using the univariate CPH model. To plot survival functions and to test for differences between AI + palbociclib and AI alone, the Kaplan-Meier estimator will be used. Given the matched nature of the study cohorts, the CPH analysis will use a robust variance estimator to account for the clustering within paired sets.

All patients will be followed from the start of therapy line through the earliest of the following: death; disenrollment from Medicare Parts A, B, or D; enrollment in an HMO plan; or end of the study database (31 December 2020). Section 7.6 discusses potential sensitivity analyses (e.g., adjusting for subsequent treatments received).

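### Time to chemotherapy: deaths without chemotherapy are censored and the endpoint is shown by Kaplan-Meier, so the curve overstates the share of patients who start chemotherapy

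*SAP*

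**What the plan says.** SAP Table 5-1 (Section 5.4) defines the endpoint as "Time in months from the study index date to first initiation of chemotherapy in any subsequent therapy lines". Death is not part of the event. The censoring rule is "Patients who did not initiate chemotherapy treatment as of last follow-up will be censored at the end of the follow-up".

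SAP 2.1 defines the end of follow-up: "All patients will be followed from their study index date through the earliest of the following: death, disenrollment from Medicare Part A", B or D, HMO enrollment, or 31 December 2020. SAP 7.3 repeats the rule: "All patients will be followed from the start of therapy line through the earliest of the following: death; disenrollment", and so on.

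On display, SAP 7.1 says that unadjusted and/or weighted "Kaplan-Meier curves will be drawn to illustrate time-to-event endpoints". It makes no exception for this endpoint.

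The objective is exploratory and conditional (SAP 2.2): "To measure time to chemotherapy, if enough follow-up time is available to assess this measure". The sections on exploratory analyses, SAP 7.4 and Protocol 9.7.2, are redacted after their opening words. No readable text in either document mentions competing risks, cumulative incidence, or a composite of chemotherapy or death for this endpoint.

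**The concern.** Kaplan-Meier treats a censored patient as someone who could still have the event later. That is a reasonable working assumption for a patient who moves to an HMO. It cannot be true of a patient who has died. With deaths censored, 1-KM estimates the chance of starting chemotherapy in a hypothetical population in which nobody dies first. It does not estimate the share of real patients who start it.

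Death is not rare here. Patients are 65 or older with stage IV disease, and follow-up can reach almost six years. A reader who takes the curve, or its median, as describing actual chemotherapy use will read it too high, and by more at later times. If mortality differs between the arms, the overstatement differs too, so part of any gap between the two curves would reflect mortality rather than chemotherapy use.

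**Working it through.** **Step 1: what the rules do together.** Table 5-1 censors at the end of follow-up anyone without chemotherapy. SAP 2.1 and 7.3 make death one of the ends of follow-up. A death without chemotherapy is therefore censored at the date of death. SAP 7.1 then applies Kaplan-Meier.

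**Step 2: direction.** Let λc be the hazard of chemotherapy and λd the hazard of death without chemotherapy, both taken as constant.

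- With deaths censored: 1-KM(t) = 1 − exp(−λc·t)
- Actual cumulative incidence: CIF(t) = λc/(λc+λd) × [1 − exp(−(λc+λd)·t)]

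For any λd > 0, 1-KM exceeds CIF at every t > 0. The direction needs no outside data.

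**Step 3: inputs for the size.** The plan states no figure to reproduce.

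- Median OS 43.2 months (AI) and 49.1 months (palbociclib + AI), with hazard ratio 0.76, from the real-world study cited in SAP 2: "49.1 [45.2-57.7] vs. 43.2 [37.6-48.0] months; hazard ratio, 0.76".
- Assumed: net chemotherapy probability at 24 months, p24 = 0.10 to 0.40, so λc = −ln(1 − p24)/24 = 0.00439 to 0.02128 per month.
- Assumed: λd = f × ln 2/median with f = 0.5 to 1.0. OS also counts deaths after chemotherapy, so f = 1 is taken as the upper end.

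**Step 4: results.**

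Lowest case: p24 = 0.10, median 49.1, f = 0.5, so λd = 0.00706. Highest case: p24 = 0.40, median 43.2, f = 1.0, so λd = 0.01605.

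| Months | Lowest: 1-KM vs CIF | Highest: 1-KM vs CIF | Excess (percentage points) |
|---|---|---|---|
| 12 | 0.051 vs 0.049 | 0.225 vs 0.206 | 0.2 to 2.0 |
| 24 | 0.100 vs 0.092 | 0.400 vs 0.337 | 0.8 to 6.3 |
| 36 | 0.146 vs 0.130 | 0.535 vs 0.421 | 1.7 to 11.4 |
| 48 | 0.190 vs 0.162 | 0.640 vs 0.475 | 2.8 to 16.5 |

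**Step 5: difference between arms.** With the same λc in both arms, the excess differs between arms as follows.

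| Contrast in λd | 24 months | 36 months |
|---|---|---|
| Medians 43.2 vs 49.1 | 0.1 to 0.7 points | 0.2 to 1.2 points |
| AI arm at 43.2, hazard ratio 0.76 | 0.2 to 1.4 points | 0.4 to 2.4 points |

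**Step 6: sensitivity to the assumptions.** The 50% floor for f has no source. Lowering it to 30% (λd = 0.00424, p24 = 0.10, median 49.1) moves the 24-month floor from 0.8 to 0.5 points.

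A second set of assumptions for the AI arm used a chemotherapy median of 24, 40 or 60 months and f from 0.3 to 1.0. It gives an excess of 1.3 to 7.6 points at 24 months and 2.6 to 13.1 at 36. A simulation of 400,000 patients with administrative censoring, at a chemotherapy median of 40 months and f = 0.5, agreed with the closed form within 0.1 point (24 months: 34.0% vs 31.1%, against 34.0% vs 31.2%).

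**The case against.** The strongest objection is redaction. The methods for this endpoint belong in SAP 7.4 and Protocol 9.7.2, and neither can be read. A competing-risk method may be there, so nobody can say that the plan lacks one. This stands, and it limits the point to the readable text. It does not remove it: Table 5-1 and 7.1 as written treat death and disenrollment alike, and would still need to agree with 7.4.

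Second, 7.1 is a general sentence about illustrative curves. It does not mention 1-KM or promise chemotherapy probabilities, and the medians and landmark probabilities in 7.3 are specified for OS. That is so, and the point is therefore conditional on how the curve is read. Yet a time-to-chemotherapy curve invites exactly that reading.

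Third, censoring deaths is legitimate when the target is the cause-specific hazard, and a Cox model fitted that way is valid. This stands in full. The problem is confined to the absolute-risk display and to an estimand that is not labelled.

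Fourth, the size rests on chosen hazards, and the larger late figures concern few patients. With data ending on 31 December 2020, only those indexed by the end of December 2016 can reach 48 months. The 12- and 24-month figures are the more relevant ones, because those are the landmarks that the SAP gives as examples for OS.

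**Conclusion.** The point holds, as a minor one. Under the readable rules, the complement of the planned curve overstates the proportion of patients starting chemotherapy. The direction follows from the documents alone. The size is illustrative: 0.8 to 6.3 percentage points at 24 months, growing with time, and at most about 1.4 points of spurious difference between arms at 24 months. It depends on constant hazards, the assumed chemotherapy probability, the assumed share of deaths that occur without chemotherapy, and OS medians taken from a different data source. The endpoint is exploratory and conditional on enough follow-up, and the primary OS analysis is not affected. If the redacted section already treats death as a competing event, what remains is an inconsistency of wording between sections.

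**What to change.** - **Table 5-1:** name death before chemotherapy as a competing event. Limit censoring to patients who are alive without chemotherapy at disenrollment from Part A, B or D, at HMO enrollment, or on 31 December 2020.
- **SAP 7.1:** for this endpoint, replace the Kaplan-Meier display with Aalen-Johansen cumulative incidence, sIPTW-weighted wherever the Kaplan-Meier curve would have been weighted.
- **Any Cox model that censors deaths:** label its hazard ratio as cause-specific.
- **Optional:** add chemotherapy-free survival (chemotherapy or death, whichever comes first), for which Kaplan-Meier is valid.
- **If SAP 7.4 already specifies such a method:** make Table 5-1 and 7.1 agree with it.

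The cost is a sentence in each of the two places and a little more programming, with no new data. The reported chemotherapy percentages will be lower than those from 1-KM.

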5.5 EXPOSURE VARIABLES AND COVARIATES

The exposure and other covariates to be analyzed as part of the study objectives and associated definitions are described in [Table 5-2](#). For covariates, categories may be further combined if appropriate for statistical purposes.

Table 5-2. Definitions of Exposure Variables

Variable	Role/objective	Definition
Exposure variables		
1L treatment type	Primary	
Patients initiating 1L therapy with one of the following regimens (to be identified in the Prescription Drug Event file using the generic drug names and HCPCS procedure codes, as applicable):
 
 • Palbociclib + AI • AI alone 
AI will include the following individual agents:
 
 • Anastrozole (HCPCS code: S0170) • Letrozole (HCPCS code: N/A) • Exemestane (HCPCS code: S0156) 
Therapy line definition: For each patient, the 1L therapy will be defined as all agents administered within a 60-day period after treatment initiation. The 1L therapy will start on the date the first agent will be

PFIZER CONFIDENTIAL

Variable	Role/objective	Definition
		administered (or filled) and will be considered to have ended upon occurrence of the earliest of any of the following: treatment switch to a new regimen or a gap of more than 90 days in administration or refill of any of the 1L regimen drugs. The start and end dates of the second and subsequent therapy lines will be defined in a similar fashion. The rules defining "treatment switch to a new regimen" are presented in Appendix 1.
Subsequent treatment	Exploratory	All subsequent treatment lines for patients initiating 1L therapy with palbociclib + AI or AI alone, including a description of treatment switch from AI alone to palbociclib + AI.
Control variables/covariates		
Tumor grade at diagnosis	Clinical characteristic (assessed at mBC diagnosis)	The tumor grade will be summarized as below: 
 • Grade 1 (lowest grade; well differentiated) • Grade 2 • Grade 3 • Grade unknown
Metastatic site involvement at diagnosis	Clinical characteristic (assessed at mBC diagnosis)	The SEER-defined metastatic site variables will be used to describe involvement of any of the following sites at diagnosis: 
 • Bone • Brain • Liver • Lung • An additional variable will be created to describe presence of visceral metastases using the composite of liver and lung.
NCI Comorbidity Index (NCICI) Score	Clinical characteristic (assessed within the 6 months period before index date)	The comorbidity burden during the 6-month baseline period will be assessed using the NCI's comorbidity index, which is described in the Klabunde adaptation of the Charlson Comorbidity Index, version 2021 (Klabunde et al., 2007; National Cancer Institute, 2023a). NCICI scores will be reported as continuous and categorical variables: 
 • Score 0 • $0 < \text{Score} \leq 1$ • $\text{Score} > 1$

PFIZER CONFIDENTIAL

CT24-WI-GL03-RF03 2.0 Non-Interventional Statistical Analysis Plan For Secondary Data Collection Study
 01-Jun-2020
 Page 13 of 29

Variable	Role/objective	Definition
		
The specific comorbidities represented in the NCICI include the following:
 
 • Acute myocardial infarction • History of myocardial infarction • Congestive heart failure • Peripheral vascular disease • Cerebrovascular disease • Chronic obstructive pulmonary disease • Dementia • Paralysis (hemiplegia or paraplegia) • Diabetes without complications • Diabetes with complications • Renal disease • Mild liver disease • Moderate/severe liver disease • Peptic ulcer disease • Rheumatologic disease • AIDS
Age	Demographics (assessed at mBC diagnosis and at index date)	
Age at diagnosis will be assessed as continuous and categorical variables:
 
 • 65-69 years • 70-74 years • 75-79 years • ≥ 80 years
Year of diagnosis	Demographics (assessed at mBC diagnosis)	
Year of de novo mBC diagnosis will be described as a categorical variable:
 
 • 2015 • 2016 • 2017 • 2018 • 2019

PFIZER CONFIDENTIAL

Variable	Role/objective	Definition
Race	Demographics (assessed at mBC diagnosis)	
Race will be defined using the SEER Race Recode variable and categorized as follows:
 
 • American Indian/Alaska native • Asian or Pacific Islander • Black • White • Other or unknown 
These categories may be further combined for statistical purposes as below:
 
 • White • Non-White
Origin/ethnicity	Demographics (assessed at mBC diagnosis)	
Ethnicity will be defined using the SEER Origin Recode variable defined by the NAACCR Hispanic Identification Algorithm (NHLA) and categorized as follows:
 
 • Hispanic (Spanish-Hispanic-Latino) • Non-Hispanic (non-Spanish-Hispanic-Latino)
Race-ethnicity	Demographics (assessed at mBC diagnosis)	
Race will be defined using the SEER Race Recode variable, and ethnicity will be defined using the SEER Origin Recode variable defined by the NAACCR Hispanic Identification Algorithm (NHLA) and categorized as follows:
 
 • American Indian/Alaska native/unknown • Hispanic • Non-Hispanic Asian or Pacific Islander • Non-Hispanic Black • Non-Hispanic White

PFIZER CONFIDENTIAL

CT24-WI-GL03-RF03 2.0 Non-Interventional Statistical Analysis Plan For Secondary Data Collection Study
 01-Jun-2020
 Page 15 of 29

Variable	Role/objective	Definition
Marital status	Demographics (assessed at mBC diagnosis)	
Marital status will be categorized as follows:
 
 • Married • Not married 
 ◦ Single (never married) ◦ Unmarried living with domestic partner ◦ Divorced ◦ Separated ◦ Widowed • Unknown 
These categories may be further combined for statistical purposes as below:
 
 • Single (never married) • Married/unmarried living with domestic partner • Divorced/separated/widowed • Unknown
Geographic region	Demographics (assessed at mBC diagnosis)	
The geographic region of patients' county of residence will be defined according to the rural-urban continuum code (version year 2013) and categorized as follows:
 
 • Big metro: Counties in metropolitan areas ≥ 1 million population • Metro: Counties in metropolitan areas of 250,000 to 1 million population • Urban: Counties in metropolitan areas of < 250,000 population • Less urban: Nonmetropolitan counties adjacent to a metropolitan area • Rural: Nonmetropolitan counties not adjacent to a metropolitan area 
These categories may be further combined for statistical purposes as below:
 
 • Large urban (big metro and metro areas) • Small urban (urban and less urban areas) • Rural

Variable	Role/objective	Definition
Household income	Demographics (assessed using the latest available ACS data: 2008-2012)	The median household income based on patients' census tract of residence will be defined according to American Community Survey data (2008-2012). Data will be categorized using quartile distribution as follows: 
 • Quartile 1 (e.g., < \$55,000) • Quartile 2 (e.g., \$55,000-\$64,999) • Quartile 3 (e.g., \$65,000-\$74,999) • Quartile 4 (e.g., \$75,000+) • Missing/unknown
LIS coverage	Demographics (assessed during 6 months before index date)	Patient's enrollment in an LIS plan during the 6-month baseline period will be assessed and summarized as a binary variable: 
 • Any LIS coverage • No LIS coverage
Medicaid (dual) eligibility	Demographics (assessed as available in the data at mBC diagnosis or treatment) [Not to be used in propensity score model]	Medicare with Medicaid (dual) eligibility status will be summarized according to primary payer/insurance carrier at the time of initial diagnosis and/or treatment at the reporting facility: 
 • Medicaid • No Medicaid

1L = first line; ACS = American Community Survey; AI = aromatase inhibitor; HCPCS = Healthcare Common Procedure Coding System; LIS = low-income subsidy; mBC = metastatic breast cancer; N/A = not applicable; NAACCR = North American Association of Central Cancer Registries; NCI = National Cancer Institute; NCICI = NCI Comorbidity Index; NHIA = NAACCR Hispanic Identification Algorithm; SEER = Surveillance, Epidemiology, and End Results.

